2.3.2.3 Two- Dimensional Echocardiography with Complete Doppler Analysis

A complete two-dimensional (2D) echo will be performed utilizing a commercially available GE Vivid-9 or Philips iU33 Echocardiography System. A standard imaging protocol will be performed. The following linear echocardiographic measurements will be obtained (by 2D or M-mode) in both end-diastole and end-systole: left ventricular (LV) internal dimension, septal wall thickness (SWT), and posterior wall thickness (PWT). Quantification of LV mass will be derived by the formula of Devereux RB et al²⁹ and by three dimensional-guided modified biplane Simpson's rule^{30,31}. LV and left atrial (LA) volumes (systolic and diastolic) will be measured by the biplane method of discs (modified Simpson's rule). LV ejection fraction and LA function will be calculated from these volume measurements.

2.3.2.4 Electrocardiogram

A standard 12 lead electrocardiogram will be performed with standard instrument sensitivity of 10 mm = 1 mV. A sum of precordial voltage (sum of S wave in lead V1 plus R wave in lead V₅ or V₆ [SV1 + RV₅ or V₆]) will be calculated for all electrocardiograms. This sum will be used to compare data from patients with myocardial retention of ^{99m}Tc-PYP from controls. LVH will be defined when this sum is greater than 35 mm. When the sum was less than 15 mm, low voltage in the precordial leads is present. Additional criteria to define low voltage only in the limb leads include no QRS deflection greater than 5 mm in any limb lead and low voltage in all leads is present when the average voltage in the three limb leads is <5 mm, and the average voltage in the chest leads is <10 mm.³⁷ Finally, the mass: voltage ratio will be calculated using the LV mass divided by the sum of S wave in lead VI plus R wave in lead V₅ or V₆ [SV1 + RV₅ or V₆]. The ECG tracings will be scanned and uploaded in electronically.

2.3.2.5 Blood and saliva testing

During the study visit, subjects will undergo a blood draw with no more than 25 cc of blood drawn and a cheek swab or saliva swab. This blood will be sent for testing for serum kappa and lambda free light chains and serum protein electrophoresis with immunofixation. These tests will assess for the substrate for light chain amyloidosis which can mimic ATTR-CA. If patients are found to have a monoclonal gammopathy, they will be referred for further management by a physician outside the study. In addition, a sample may be drawn for biobanking and TTR genetic testing at the investigator's discretion if preliminary testing is concerning for cardiac amyloidosis.

2.3.2.6 Follow-Up Protocol

Participants will be called after the completion of testing by an investigator to counsel them on the results of their testing. In the event that they are diagnosed with cardiac amyloidosis or are found to have other serious pathology, the following steps will be taken:

- The patient will be told the results of their testing and an appropriate referral for follow-up made. If the patient has a treating physician, they will be instructed to go to their physician for further care as needed. In the event of an amyloidosis diagnosis, the patient will be referred to the Columbia University Amyloidosis Center for further care. If they do not have a treating physician, they will be given an appropriate referral for further care.
- A letter will be generated and mailed to the patient and uploaded to the patient's medical record. This letter will state the results of their testing and recommend that the patient see a physician for further care.

2.3.3 Hypotheses

Specific Aim 1: To prospectively validate that deep learning models can detect undiagnosed cardiac amyloidosis in large populations of patients undergoing cardiac testing

The specific hypothesis is that by applying an cardiac amyloidosis deep learning detection model to the entire Columbia database of patients, we will identify a group of patients at highest likelihood of having undiagnosed cardiac amyloidosis. We will validate the model by prospectively scanning 100 subjects with cardiac amyloid scintigraphy with $\geq 20\%$ being diagnosed with cardiac amyloidosis, a percentage that would potentially allow a cost-effective, wide-scale screening approach. The prevalence of cardiac amyloidosis in an unselected population of older adults who have undergone cardiac testing with an echocardiogram and ECG is unknown but is likely significantly less than 15% based on studies of more selected populations such as older adults with heart failure⁵ and aortic stenosis.³⁸ Based on our model's ability to accurately distinguish between cardiac amyloidosis cases and normal patients in a cohort of patients undergoing cardiac amyloid scintigraphy scanning, we predict that $\geq 20\%$ of patients identified by the model as being of high probability of having cardiac amyloidosis will be diagnosed with cardiac amyloidosis.

Specific Aim 2: To incorporate additional data to improve the deep learning model's detection of cardiac amyloidosis.

Hypothesis 1: Incorporating raw ECG waveform data and clinical variables such as orthopedic manifestations, e.g. carpal tunnel syndrome and spinal stenosis, associated with ATTR-CA, will improve the model's predictive capacity by 5% compared to currently used data in Aim 1.

Hypothesis 2: These deep learning models will allow identification of at least one key variable not currently associated with ATTR-CA that can inform future amyloidosis research.

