2.2 Rationale

This study aims to create an automated, end-to-end pathway which can accurately identify patients at high probability of having cardiac amyloidosis who are currently undetected. The specific analytical objectives of this aim include the following: (1) use a deep learning model to identify 100 patients at high probability of having undiagnosed cardiac amyloidosis and invite them for diagnostic testing with the hypothesis that $\geq 20\%$ will be found to have cardiac amyloidosis. A positive detection rate of this amount could likely allow for effective active case surveillance in at-risk populations and result in adoption of the technology at other institutions, potentially leading to thousands of additional diagnoses being made each year.

2.3. Database Structure:

Our informatics pipeline uses three major sources of data for this study: (1) a database of cardiac amyloidosis cases and controls, (2) an ECG database, and (3) an echocardiogram database (Figure). The cardiac amyloidosis cases and controls database includes 753 consecutive patients who underwent 99mTc-PYP scanning. Using this database, we identified 212 patients with definite ATTR-CA by consensus criteria and 455 patients with no cardiac amyloidosis.^{18, 19} A manuscript analyzing these patients in detail is in revisions. Additional lists of patients with AL-CA and ATTR-CA were obtained from department records. The ECG database includes over 2 million ECGs. At Columbia University Irving Medical Center, ECGs are stored and analyzed digitally using the MUSE Cardiology Information System (GE Healthcare, Chicago, IL, United States). For each individual ECG, the MUSE database stores high level, quantitative data in a matrix format for all 12 ECG leads in addition to the physician text-based report. Quantitative data includes interval length (such as PR,

[figure not shown]

Figure 2. Visual representation of database information. Our database has three significant inputs (ECG, abstracted clinical information, and echocardiography) which are used in our deep learning model to predict one output (presence or absence of ATTR-CA, typically as diagnosed by 99mTc-PYP scanning).

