Figure 4: Aim 2. With the addition of raw ECG waveforms electronic health record information to pre-existing data in our pipeline, we aim to improve the predictive capacity of our model and potentially identify novel clinical associations for ATTR-CA.

2.9. Orthopedic manifestations: Previous work has shown that the orthopedic manifestations of carpal tunnel syndrome,²² spinal stenosis,^{23, 24} and hip and knee osteoarthritis requiring arthroplasty²⁵ can precede the diagnosis of cardiac amyloidosis by up to 5-7 years. Pathophysiologically, the carpal tunnel and multiple areas in the spine are small, compressed spaces. As a result, relatively little amyloid deposition can lead to significant symptoms, and nerve involvement may accentuate pain syndromes. The period of time when patients have symptomatic carpal tunnel syndrome, spinal stenosis, or osteoarthritis but before they have developed symptomatic heart disease could be an ideal time to diagnose systemic amyloidosis and initiate treatment. Preliminary work at our institution using manual chart abstraction has demonstrated that these orthopedic manifestations are more common in ATTR-CA patients than in controls (to be presented at International Society of Amyloidosis 2020 meeting). In order to incorporate these features in our model, we will collect electronic health record data on orthopedic manifestations as documented by Diagnosis Related Group codes, past medical and surgical history, and problem lists all patients seen in the CUIMC system. We will then incorporate this data into our deep learning models with two significant goals: (1) assess improvement in model's capacity to detect ATTR-CA, and (2) determine if it is possible to develop a model which prioritizes detection of patients with earlier cardiac involvement.

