2.10. Electrocardiogram waveform analysis: Our current deep learning model uses tabular ECG data from the MUSE system documenting stored voltages and deflections. We believe that improvements to the ECG portion of this model are possible by adding raw waveform data. The waveforms on a 12 lead ECG are feature-rich with ~50,000 discrete data points as opposed to ~700 data points that are stored in the tabular data. Prior work has shown that deep learning analysis of 12 lead ECGs can identify significant pathology that would be essentially invisible to a human interpreter.¹⁶ We plan to include the raw ECG waveform data in the NAC/NALU models as well as develop a convolutional neural network (CNN) model based primarily of the waveform data. The CNN model will be developed similarly using the same train/development/test splits previously discussed. We will utilize the Adam optimizer and binary cross entropy as the loss function. We will assess convolutions across a single lead as well as a pooled convolution across all leads. We will then evaluate performance characteristics of the model with probability thresholds of 1%, 5%, 10%, 20%, 50%, and 75%. By adding raw waveforms data, we aim to increase the AUC of our model to >0.90.

2.11. Testing for novel clinical associations by using deep learning: The most promising aspect of NAC/NALU-based deep learning models is that by learning generalizable numerical representations, there is hope to build neural networks that are explainable with simple and sparse arithmetic of raw input features. Compared to other deep learning models, the output is more interpretable and is essentially an equation. The addition of a Laplacian-regularized filter pushes the model to make values more binary, either including them entirely or not at all. Instead of finely tuning hundreds of knobs, the model is asked to flip on switches of fewer input variables that matter.

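### Aim 2's two numerical targets, a 5% gain on an unnamed metric and an AUC level above 0.90, do not establish that the added data improve the model

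*Combined protocol and SAP*

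**What the plan says.** Two sections of the protocol set numerical targets for Aim 2.

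- Section 2.3.3, Specific Aim 2, Hypothesis 1: raw ECG waveforms plus clinical variables such as orthopedic manifestations will improve the model's "predictive capacity by 5% compared to currently used data in Aim 1". No metric is named, and 5% is not said to be absolute or relative.
- Section 2.10: "By adding raw waveforms data, we aim to increase the AUC of our model to >0.90". This is a level, and it concerns the waveform data.

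Section 2.9 adds a goal for the orthopedic data, to "assess improvement in model's capacity to detect ATTR-CA", again with no metric or size.

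Several new models are foreseen in section 2.10: "We plan to include the raw ECG waveform data in the NAC/NALU models as well as develop a convolutional neural network (CNN) model", and for the CNN, "We will assess convolutions across a single lead as well as a pooled convolution across all leads". That makes at least three candidates. Performance is then to be described at six probability thresholds from 1% to 75%.

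The section on traditional statistical modeling sets a 70/15/15 split into training, development and test data by patient, and also 5-fold cross-validation. It does not say how the two combine. The new models use the same splits. For Aim 2 the protocol states no current AUC, deciding model, paired comparison or confidence interval.

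**The concern.** Aim 2 asks whether extra data make the model better. Answering that requires a comparison of two models in the same patients, on one measure, with a statement of uncertainty. The 5% target implies a comparison but leaves the measure and scale open. The 0.90 target names the measure but drops the comparison: a model no better than the current one can pass it by sampling variation if the current AUC is already near 0.90.

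What is at stake is the claim that waveforms and clinical variables help. Section 2.12 would carry the Aim 2 model into a repeat trial aimed at earlier-stage disease, so a gain that is not real would be taken forward.

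**Working it through.** **Inputs from the protocol.** Section 2.3 (Database Structure): "we identified 212 patients with definite ATTR-CA by consensus criteria and 455 patients with no cardiac amyloidosis", so 212 + 455 = 667 labelled patients. A 15% test set has 0.15 × 212 ≈ 32 cases and 0.15 × 455 ≈ 68 controls. There is no Aim 2 sample size, power or alpha to reproduce.

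**Assumptions.** Current AUC (not stated; below 0.90 is implied by section 2.10), correlation between model scores within cases and within controls (0.5 to 0.9), and three new candidates.

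**1. Where the two cut-offs coincide, if both are read as AUC.** Absolute 5%: 0.90 − 0.05 = 0.85. Relative 5%: 0.90 / 1.05 = 0.857. At any other baseline the verdicts differ only when the new AUC falls between the cut-offs:

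| Current AUC | 5% cut-off, relative | 5% cut-off, absolute | Verdicts differ (relative reading) |
|---|---|---|---|
| 0.84 | 0.882 | 0.89 | 0.882 to 0.90 |
| 0.88 | 0.924 | 0.93 | 0.90 to 0.924 |

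So 0.80 rising to 0.86 meets the 5% target on either scale (cut-offs 0.84 and 0.85) and misses 0.90. A rise from 0.88 to 0.91 does the reverse.

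**2. Precision of one AUC.** Hanley-McNeil, with m cases and n controls: SE² = [A(1−A) + (m−1)(Q1−A²) + (n−1)(Q2−A²)] / (mn), where Q1 = A/(2−A) and Q2 = 2A²/(1+A). With m = 32 and n = 68, the SE is 0.046 at A = 0.85, 0.0445 at 0.86 and 0.0416 at 0.88. The 95% half-width at 0.85 is 1.96 × 0.046 ≈ 0.09, wider than a five-point target.

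**3. Chance of exceeding 0.90 with no gain, normal approximation, one model.** At 0.86: 1 − Φ(0.04/0.0445) ≈ 0.18. At 0.88: 1 − Φ(0.02/0.0416) ≈ 0.32.

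**4. Simulation with no true gain.** Binormal scores, the current model and three new models all with the same true AUC (0.86 or 0.88), correlation 0.5 to 0.9.

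| Event | Test set, 32/68 | All 667, pooled out-of-fold |
|---|---|---|
| AUC >0.90, one new model | about 15-32% | about 7% at 0.88; 1% or less at 0.86 |
| AUC >0.90, best of three | about 23-54% | up to about 16% at 0.88; 1% or less at 0.86 |
| 5% relative AUC gain, one new model | about 2-15% | about 0-2.5% |

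The runs were not restricted to those in which the current model's observed AUC was below 0.90. The pooled column treats out-of-fold predictions as if they came from one model.

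**5. What a paired interval would deliver.** SE of the difference = √(SE₁² + SE₂² − 2r·SE₁·SE₂). For a true rise from 0.85 to 0.90 on 32/68, SE₁ = 0.0458 and SE₂ = 0.0383. With a correlation r between the two AUCs of 0.5, 0.7 and 0.9, the SE is 0.043, 0.033 and 0.020, and the 95% half-width about 0.083, 0.065 and 0.040. The chance that the lower limit exceeds zero is then about 22%, 32% and 70%. On all 667 patients it is about 86% at r = 0.5 and 97% at r = 0.7.

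**The case against.** The two targets need not be rival rules for one test. Section 2.10 states an aspiration for adding waveforms; section 2.3.3 states a hypothesis for waveforms plus clinical variables. Different inputs may have different targets. Aim 2 is model development, not the primary objective. The protocol also has safeguards: identical splits, a development set, regularization and 5-fold cross-validation. It mentions further patient lists without numbers, so 32/68 may understate the data. Much of this stands, and it limits the point.

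A reader might infer three stronger things that the documents do not support.

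- *That the targets generally give opposite verdicts.* Different cut-offs are not different verdicts. The verdicts part only in the window shown above.
- *That almost any outcome could be reported as success.* On the AUC reading, with a true AUC of 0.86, no gain and one new model on the test set, neither target is met in about 77-82% of runs. A much higher rate requires predictive capacity to mean any of some 31 measures across the six thresholds, and the protocol never ties those thresholds to Hypothesis 1.
- *That the best model will be picked on test results.* The protocol does not say so. The best-of-three figures show what would follow if it were.

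The safeguards do not answer the remaining point. None of them names the metric, the scale or the deciding model, and none turns the 0.90 level into a comparison.

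**Conclusion.** The concern holds in a limited form. As written, meeting either Aim 2 target does not show that the added data improve the model: one target has no named metric or scale, the other has no comparator.

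The size depends on the unstated current AUC and on the evaluation set. If the test set alone is used and the true AUC is 0.86 to 0.88, a model with no gain passes 0.90 about one time in seven to one time in three. With cross-validated predictions pooled over 667 patients, a spurious 5% AUC gain is rare, but the 0.90 level can still be passed without a gain when the baseline is close to it. At a baseline of 0.80, passing 0.90 by chance is unlikely even on the test set (about 1% with one new model). Aim 1 is untouched. The change should be made, but it does not bear on the trial's main result.

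**What to change.** In sections 2.10 and 2.3.3, judge Aim 2 by one criterion: the paired difference in AUC, augmented minus current model, in the same patients, with a 95% confidence interval. In addition:

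- State whether 5% is absolute or relative, and give the current model's AUC.
- Name the evaluation set: the held-out test set or pooled out-of-fold predictions.
- Compare one augmented model, chosen on training and development data only.
- Say what the interval must exclude. Requiring the lower limit of a two-sided 95% interval to exceed zero holds false success near 2.5%. Requiring only that the point estimate reach the 5% mark would succeed about half the time when the true gain is exactly that size.
- Report AUC above 0.90, the six-threshold results and the other candidate models as descriptive.

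The cost is wording in two sections and a small amount of analysis, since the shared splits already pair the models. The sponsor gives up choosing the metric or model afterwards. If only the test set of about 100 patients is used, the interval will be wide (half-width about 0.04 to 0.08 in the example above), which is a reason to settle the evaluation set now.
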